3.9.1 Screen failures

Screening failures are patients who do not fulfil the eligibility criteria for the study, and therefore must not be randomised. These patients should have the reason for study withdrawal recorded as 'Screen failure' (the potential patient who does not meet one or more criteria required for participation in a study, this reason for study withdrawal is only valid for not randomised patients). 'Failure to meet randomisation criteria' should be selected for an indication that the patient has been unable to fulfil/satisfy the criteria required for assignment into a randomised arm.

3.9.2 Withdrawal of the informed consent

Patients are free to withdraw from the study at any time (IP and assessments), without prejudice to further treatment.

A patient who withdraws consent will always be asked about the reason(s) and the presence of any AEs. The Investigator will follow up AEs outside of the clinical study.

If a patient withdraws from participation in the study, then his/her enrolment/randomisation code cannot be reused. Withdrawn patients will not be replaced.

If a patient withdraws consent, they will be specifically asked if they are withdrawing consent to:

- further participation in the study including any further follow up (eg, survival calls)
- withdrawal of consent to the use of their study generated data
- withdrawal to the use of any samples (see Section 5.7.4)

The status of ongoing, withdrawn (from the study) and “lost to follow-up” patients at the time of an OS analysis should be obtained by the site personnel by checking the patient notes, hospital records, contacting the patient’s general practitioner and checking publicly available death registries. In the event that the patient has actively withdrawn consent to the processing of their personal data, the vital status of the patient can be obtained by site personnel from publicly available resources where it is possible to do so under applicable local laws.

3.10 Discontinuation of the study

The study may be stopped if, in the judgment of AstraZeneca, study patients are placed at undue risk because of clinically significant findings that:

- meet individual stopping criteria or are otherwise considered significant
- are assessed as causally related to study drug,
- are not considered to be consistent with continuation of the study

Regardless of the reason for termination, all data available for the patient at the time of discontinuation of follow-up must be recorded in the CRF. All reasons for discontinuation of treatment must be documented.

In terminating the study, the Sponsor will ensure that adequate consideration is given to the protection of the patients’ interests.

4. STUDY PLAN AND TIMING OF PROCEDURES

The scheduled Screening Part 1 and Screening Part 2 assessments are summarized in [Table 2](#) and [Table 3](#), respectively. The scheduled assessments for on-study treatment and study discontinuation are summarized in [Table 4](#) for the olaparib monotherapy arm and the ceralasertib+olaparib arm and in [Table 5](#) for the AZD1775+olaparib arm. Patients on treatment in April 2019 when the AZD1775+olaparib arm was closed will be offered the opportunity to continue treatment of olaparib monotherapy at their next treatment cycle at the approved dose (300 mg bd) and should follow [Table 5](#) continuing treatment on a 21-day cycle.

Table 2 Study schedule – Screening Part 1

Day	Up to Day -28
Informed consent	X
Demographics	X
Medical and surgical history ^a	X
Inclusion criteria # 1, 2, 4, 5, 9, 10, 14 (see Section 3.1)	X
Exclusion criteria # 1, 3, 4, 5, 6, 7, 8, 15, 16, 17, 18, 19, 20 (see Section 3.2)	X
ECOG PS (0-1)	X
Pregnancy test ^b	X
FFPE tumour tissue block or sections for FMI Lynparza HRR assay ^c	X

^a This should include any previous cancer therapies (including radiotherapy an response to current chemotherapy regimen) as well as any history of blood transfusion within 120 days from start of study treatment, with reasons (eg, bleeding or myelosuppression).

^b Women of child-bearing potential must have a negative urine or serum pregnancy to be eligible for screening. If results are positive, the patient is ineligible for randomisation in the study.

^c FFPE tumour tissue blocks are required, but if not available, tissue sections are accepted. At least twenty (20) (thirty [30] preferable) unstained sections without cover slips must be submitted to ensure sufficient material for the prospective Lynparza HRR testing to determine study eligibility. Patients must have a confirmed qualifying HRR mutation status to be eligible for the study. Patients with known HRR status and with documented confirmation of the qualifying mutation may enrol (see Section 5.7).

Table 3 Study schedule – Screening Part 2 (Visit 1)

Day	-28 to 0
Informed consent	X
Demographics	X
Medical and surgical history ^a	X
Inclusion/exclusion criteria	X
ECOG PS (0-1)	X
Vital signs (includes BP, pulse and temperature)	X
Haematology/clinical chemistry/coagulation ^b	X
Urinalysis ^c	X
Pregnancy test ^d	X
Physical examination including weight ^e	X
Tumour assessment (RECIST 1.1) ^f	X
ECG ^g	X
AEs (from time of consent) ^h	X
Concomitant medications including blood transfusions	X
CCI ██████████	X
CCI ██████████	X
Blood for circulating tumour cells	X
Blood sampling for CCI ██████████ analysis ⁱ	X

- ^a This should include any previous cancer therapies (including radiotherapy an response to current chemotherapy regimen) as well as any history of blood transfusion within 120 days from start of study treatment, with reasons (eg, bleeding or myelosuppression).
- ^b Coagulation test should be performed at screening and sequentially if clinically indicated. For a list of all required laboratory tests please refer to Section 5.2.1.
- ^c Urinalysis should be performed at screening. After screening, urinalysis will only be required if clinically indicated.
- ^d Women of child-bearing potential must have a negative urine or serum pregnancy test within 28 days prior to starting treatment and a confirmatory test before treatment on Day 1. If results are positive, the patient is ineligible/must be discontinued from the study.
- ^e Physical examination should be done as per schedule but does not need to be recorded in the eCRF after the baseline assessment. Any clinically significant changes not unequivocally related to disease progression should be recorded as AEs.
- ^f Baseline RECIST 1.1 assessments will be performed using CT scans of the chest, abdomen and pelvis (or MRI where CT is contraindicated) and should be performed no more than 28 days before the start of study treatment and as close as possible to the start of study treatment and prior to randomisation. Brain CT scan/MRI at baseline should be done for patients with known history of brain metastatic disease.
- ^g ECGs are required within 7 days prior to starting study treatment. ECGs should be performed in triplicate.
- ^h When an AE for nausea and vomiting occurs, an additional eCRF page will require completion.
- ⁱ Blood samples for CCI ██████████ analysis (eg, CCI ██████████) to be taken during screening.
- PBMC=peripheral blood mononuclear cell

Table 4 Study schedule - on study treatment and discontinuation: olaparib monotherapy arm and ceralasertib+olaparib arm

Following the data cut off for the final analysis for PFS for a given stratum, data collection in the eCRF for that stratum will be reduced. It is recommended that the study schedule is followed as outlined below however data entry will be restricted to IP dispensation and accountability, safety laboratory assessments, pregnancy test, AEs and SAEs (see Table 6 for data collection requirement and section 9.3). Following the final analysis for PFS (primary) data cut off for a given stratum exploratory sample collection will stop for that stratum with the exception of the required blood sample for **CCI** analysis at the time of progression. The tumour biopsy (optional) at the time of progression should also be collected.

Visit Name	On treatment Cycle 1	2	3	4	Subsequent on treatment visits (every 28 days)*	Study treatment discontinued	Follow-up 30 days after last dose of study medication	Survival follow-up
Visit Number		2	3	4	Visit No. 5 onwards			
Day	1	7	15	±3d	Cycle X, Day 1^m	±7d	+7d	Every 8 weeks ±7d
Visit Window		±3d			±3d	±7d	+7d	
Randomisation ^a	X							
ECOG PS	X				X	X		
Vital signs (includes BP, pulse and temperature)	X ^b				X	X	X	
Haematology/clinical chemistry ^c	X ^b	X		X	X	X	X	
Physical examination and weight ^d	X				X	X	X	
Tumour assessment (RECIST 1.1) ^e					X	X		
ECG ^f	X ^f	X		X	X ^f	X	X	

Visit Name	On treatment Cycle 1			Subsequent on treatment visits (every 28 days)*	Study treatment discontinued	Follow-up 30 days after last dose of study medication	Survival follow-up
Visit Number	2	3	4	Visit No. 5 onwards			
Day	1	7	15	Cycle X, Day 1 ^m			Every 8 weeks
Visit Window			±3d	±3d	±7d	+7d	±7d
Pregnancy test ^e	X			X		X	
Adverse events ^h	X	X	X	X	X	X	
Concomitant medications including blood transfusions	X	X	X	X	X	X	
Anti-cancer therapies							X
CCI	X			X	X		
Optional tumour biopsy at progression					X ⁱ	(Progression only)	
Blood sample for PK analysis ^k	X	X					
CCI	X	X	X	X	X	X	
				(Cycle 2 only)	(Progression only)		
Blood for circulating tumour cells	X			X	X	X	
				(Cycle 2 only)	(Progression only)		

Visit Name	On treatment Cycle 1	Subsequent on treatment visits (every 28 days)*	Study treatment discontinued	Follow-up 30 days after last dose of study medication	Survival follow-up
Visit Number	2	3	4	Visit No. 5 onwards	
Day	1	7	15	Cycle X, Day 1 ^m	Every 8 weeks
Visit Window		±3d	±3d	±3d	±7d
Blood sample for CCI analysis	X			X	X
Pharmacogenetic sample ^l	X				(Progression only)
Olaparib dosing				← Continuous twice daily dosing →	
Ceralasertib dosing				← Dosing on Days 1-7 only →	
Medication dispensed/returned/medication accountability	X			X	X
Survival					X

^a Treatment allocation will be randomised. It is recommended that patients commence study treatment as soon as possible after randomisation, and ideally within 3 days.

^b If assessment done within 7 days before starting study treatment, does not have to be repeated on Day 1 of study treatment unless the Investigator believes results have changed significantly.

^c Safety blood samples do not need to be repeated on Day 1 of study treatment if assessed at least 3 weeks after the last dose of chemotherapy but within 7 days before starting study treatment, unless the Investigator believes that it is likely to have changed significantly. Coagulation test should be performed if clinically indicated. Safety blood tests must be reviewed prior to dose administration. For a list of all required laboratory tests please refer to Section 5.2.1.

^d Physical examination should be done as per schedule but does not need to be recorded in the eCRF after the baseline assessment (except for weight which should be collected at each visit). Any clinically significant changes not unequivocally related to disease progression should be recorded as AEs.

- e RECIST 1.1 follow-up assessments will be performed every 8 weeks (± 1 week) for the first 72 weeks, then every 12 weeks (± 1 week) after randomisation until objective disease progression as defined by RECIST 1.1, irrespective of treatment decisions. Any patient who has not yet shown objective radiological disease progression at withdrawal from IP should continue to be followed as per RECIST 1.1. Follow-up assessments will include CT assessments of chest, abdomen and pelvis (or MRI where CT is contraindicated) for all patients. Any other sites at which new disease is suspected should also be appropriately imaged. If an unscheduled assessment was performed and the patient has not progressed, every attempt should be made to perform the subsequent assessments at their scheduled visits.
- f ECG assessment to be done on Day 1 of every cycle, within 1-2 hours prior to dosing. An additional baseline assessment will be conducted on Day 1, Cycle 1.
- g Pregnancy tests using blood or urine samples will be performed for women of childbearing potential within 28 days prior to the start of study treatment, on Day 1 of the study prior to commencing treatment, on Day 1 of each subsequent treatment cycle and at the follow-up visit 30 days after last dose of study medication. If results are positive, the patient must be discontinued from the study treatment immediately. Tests will be performed by the hospital's local laboratory.
- h When an AE for nausea and vomiting occurs, an additional eCRF will require completion. All ongoing AEs/SAEs and any new AEs/SAEs identified during the 30 calendar day's follow-up period after last dose of study medication must be followed to resolution.
- i To be completed every 8 weeks (± 1 week) until discontinuation of study treatment. Following the data cut off for the final analysis for PFS patients will no longer be required to complete the **CCI**.
- j Only at progression.
- k A common PK time window will be used for olaparib and ceralasertib in all patients: Cycle 1 Day 1: 2 hours (± 1 hour), 4.5 hours (± 1.5 hour) and 9 hours (± 3 hours), Cycle 1 Day 7: pre-dose, 0.5hour (± 0.5 hour), 2 hours (± 1 hour), 4.5 hours (± 1.5 hours) and 9 hours (± 3 hour).
- l The pharmacogenetic blood sample can be obtained either at the first treatment visit or after randomisation
- m If a patient has experienced a Grade 3/4 neutropenia, G4 thrombocytopenia, or a dose interruption due to haematological toxicity in a prior cycle, unscheduled Day 8 and Day 15 complete blood counts are required in subsequent treatment cycles. If no further events are experienced in the subsequent 3 consecutive cycles, then the Day 15 CBC visit can be stopped.

* Please note that the cycle length for olaparib monotherapy and ceralasertib+olaparib treatment arms will be 28 days.
PBMC=peripheral blood mononuclear cell

Table 5 AZD1775+Olaparib Schedule of Assessments (applies to Patients Randomised to this Treatment Arm who, after April 2019, continue on Olaparib monotherapy)

Following the final analysis for PFS for a given stratum, data collection in the eCRF for that stratum will be reduced. It is recommended that the study schedule is followed as outlined below however data entry will be restricted to IP dispensation and accountability, safety laboratory assessments, pregnancy test, AEs and SAEs (see Table 6 for data collection requirement and section 9.3). Following the data cut off exploratory sample collection will stop with the exception of the required blood sample for CCI analysis at the time of progression. The tumour biopsy (optional) at the time of progression should also be collected.

Visit Name	On treatment Cycle 1		On treatment Cycle 2		Subsequent on treatment visits (every 21 days)*	Scan Visit (every 8 weeks ^e)	Study treatment discontinued	Follow-up 30 days after last dose of study medication	Survival follow-up
Visit Number	2	3	4	5	6	7	8	Visit No. 9 onwards	Every 8 weeks
Day	1	8	10	15	1	8	15	Cycle X, Day 1 ^o	±7d
Visit Window	±3d		±3d		±3d		±7d		±7d
Randomisation ^a	X								
ECOG PS	X				X			X	
Vital signs (includes BP, pulse and temperature)	X ^b	X		X	X	X	X	X	X
Haematology/clinical chemistry ^c	X ^b	X	X	X	X	X	X	X	X
Physical examination and weight ^d	X				X			X	
Tumour assessment (RECIST 1.1) ^e								X	X

Visit Name	On treatment Cycle 1			On treatment Cycle 2			Subsequent treatment visits (every 21 days)*	Scan Visit (every 8 weeks ^e)	Study treatment discontinued	Follow-up 30 days after last dose of study medication	Survival follow-up
Visit Number	2	3	4	5	6	7	8	Visit No. 9 onwards	±7d	+7d	Every 8 weeks ±7d
Day	1	8	10	15	1	8	15	Cycle X, Day 1 ^o	±7d	±7d	Every 8 weeks ±7d
Visit Window	±3d			±3d			±3d	±7d	±7d	±7d	±7d
ECG ^f	X ^f	X	X	X	X ^f	X ^f	X ^f	X ^f	X	X	X
Pregnancy test ^g	X				X			X		X	
AEs ^h	X	X	X	X	X	X	X	X	X	X	X
Concomitant medications including blood transfusions	X		X	X	X			X	X	X	
Anti-cancer therapies											X
CCI	X								X	X	
Optional tumour biopsy at progression									X ⁱ	(Progression only)	
Blood sample for PK analysis ^k	X		X	X							
CCI	X		X	X	X				X	(Progression only)	

Visit Name	On treatment Cycle 1		On treatment Cycle 2		Subsequent on treatment visits (every 21 days)*	Scan Visit (every 8 weeks ^e)	Study treatment discontinued	Follow-up 30 days after last dose of study medication	Survival follow-up
Visit Number	2	3	4	5	6	7	8	Visit No. 9 onwards	
Day	1	8	10	15	1	8	15	Cycle X, Day 1 ^o	Every 8 weeks
Visit Window				±3d	±3d			±7d	±7d
Blood for circulating tumour cells	X				X			X	(Progression only)
Blood sample for CCI analysis ^m	X				X			X	(Progression only)
Pharmacogenetic sample ^p	X								
Olaparib dosing ^{**}									← Continuous twice daily dosing →
AZD1775 dosing ^{l,**}									← Dosing on Days 1-3 and 8-10 →
Medication dispensed/returned/medication accountability								X	
Survival									X

- a Treatment allocation will be randomised. It is recommended that patients commence study treatment as soon as possible after randomisation, and ideally within 3 days.
- b If assessment done within 7 days before starting study treatment, does not have to be repeated on Day 1 of study treatment unless the Investigator believes results have changed significantly.
- c Safety blood samples do not need to be repeated on Day 1 of study treatment if assessed at least 3 weeks after the last dose of chemotherapy but within 7 days before starting study treatment, unless the Investigator believes that it is likely to have changed significantly. Coagulation test should be performed if clinically indicated. Safety blood tests must be reviewed prior to dose administration. For a list of all required laboratory tests please refer to Section 5.2.1. The patient should only proceed with dosing with AZD1775 on Day 1 and Day 8 if the haematology parameters meet the dosing criteria.
- d Physical examination should be done as per schedule but does not need to be recorded in the eCRF after the baseline assessment (except for weight which should be collected at each visit). Any clinically significant changes not unequivocally related to disease progression should be recorded as AEs.
- e RECIST 1.1 follow-up assessments will be performed every 8 weeks (± 1 week) for the first 72 weeks, then every 12 weeks (± 1 week) after randomisation until objective disease progression as defined by RECIST 1.1, irrespective of treatment decisions. Any patient who has not yet shown objective radiological disease progression at withdrawal from IP should continue to be followed as per RECIST 1.1. Follow-up assessments will include CT assessments of chest, abdomen and pelvis (or MRI where CT is contraindicated) for all patients. Any other sites at which new disease is suspected should also be appropriately imaged. If an unscheduled assessment was performed and the patient has not progressed, every attempt should be made to perform the subsequent assessments at their scheduled visits.
- f All ECGs to be done in triplicate. Assessment on Day 1 of every cycle to be taken 1-2 hours prior to dosing. An additional baseline assessment will be conducted on Day 1, Cycle 1. **From April 2019 triplicate ECG no longer applies to patients who have discontinued AZD1775 but single ECGs should be taken at the stated timepoints.**
- g Pregnancy tests using blood or urine samples will be performed for women of childbearing potential within 28 days prior to the start of study treatment, on Day 1 of the study prior to commencing treatment, on Day 1 of each subsequent treatment cycle and at the follow-up visit 30 days after last dose of study medication. If results are positive, the patient must be discontinued from the study treatment immediately. Tests will be performed by the hospital's local laboratory.
- h When an AE for nausea and vomiting occurs, an additional eCRF will require completion. All ongoing AEs/SAEs and any new AEs/SAEs identified during the 30 calendar day's follow-up period after last dose of study medication must be followed to resolution.
- i To be completed every 8 weeks (± 1 week) until discontinuation of study treatment. Following the data cut off for the final analysis for PFS for a given stratum patients will no longer be required to complete the **CGI**.
- j Only at progression.
- k A common PK time window will be used for olaparib and AZD1775 in all patients: Cycle 1 Day 1: 1-3 hours, 3-6 hours and 6-12 hours; Cycle 1 Day 10: pre-dose, 0.5-1 hour, 1-3 hours, 3-6 hours and 6-12 hours. **Not applicable following CSPv6.0**
- l All patients must receive a 5-HT3 antagonist, ondansetron (Zofran) 8 mg PO or granisetron (Kytrel) 1 mg orally prior to each dose of AZD1775. Additional doses of 5-HT3 antagonist may be used if needed. In addition, dexamethasone 4 mg orally will be given with each AZD1775 dose as a minimum on the first day of dosing AZD1775 of every 3 days dosing period, unless contraindicated or not well-tolerated. Dexamethasone may be continued on further days of dosing, potentially at a lower dose. Dexamethasone or the 5-HT3 antagonist may be given by IV. Promethazine (Phenergan), prochlorperazine (Compazine), and benzodiazepine may still be used as additional adjunctive treatments during AZD1775 therapy. **Please note: aprepitant [E-mend] and fosaprepitant are not permitted due to known DDIs. No longer applicable following CSPv6.0, provided there has been a minimum washout period of 10 days since the final dose of AZD1775.** Patients should be strongly encouraged to maintain liberal oral fluid intake.

- m **CCI** sample should be taken at same visit as scan, if possible. If a **CCI** sample was taken at a scan visit not coinciding with the CxD1 visit a **CCI** sample at the CxD1 visit is not required
- n Scan visit may be tied in with CxD1 visit, using ± 7 d window, if appropriate
- o Unscheduled D8 and D15 visits with complete blood counts should be done from C3 onwards if Grade 3/4 neutropenia, G4 thrombocytopenia or a dose interruption due to haematological toxicity was experienced in a prior cycle. If no further events are experienced in the subsequent 3 consecutive cycles, then the Day 15 CBC visit can be stopped. **No longer applicable following CSPv6.0.**
- p The pharmacogenetic blood sample can be obtained either at the first treatment visit or after randomisation

* Please note that cycle length for AZD1775+olaparib treatment arm is 21 days.

** Please note that for patients on the AZD1775+olaparib treatment arm, the continuous olaparib dose will be 200 mg bd. After April 2019, all patients randomised to this treatment arm discontinued AZD1775 and were offered the opportunity to continue olaparib monotherapy at 300 mg bd on a 21-day cycle starting at the patient's next treatment cycle to ensure a minimum 10 day wash out period from AZD1775 to olaparib monotherapy 300 mg bd dosing to avoid DDI.

PBMC=peripheral blood mononuclear cell

Table 6 eCRF data entry for patients on study treatment following the data cut off for the final analysis for PFS: olaparib monotherapy arm, ceralasertib+olaparib arm and AZD1775+olaparib arm

Following the final analysis for PFS for a given stratum, data collection in the eCRF will be reduced. It is recommended that the study schedule is followed as per Table 4 and Table 5, however data entry will be restricted to IP dispensation and accountability, safety laboratory assessments, pregnancy test, AEs and SAEs (see Table 6 for data collection requirement and section 9.3). Following the data cut off exploratory sample collection will stop with the exception of a blood sample for CCI analysis and a tumour biopsy (optional) at the time of progression.

Visit Name	Subsequent on treatment visits (every 28 days)*	Study treatment discontinued	Follow-up 30 days after last dose of study medication	Survival follow-up
Visit Number	Visit No. 5 onwards			
Day	Cycle X, Day 1			Every 8 weeks
Visit Window	±3d	±7d	+7d	±7d
Haematology/clinical chemistry ^a	X	X	X	X
Pregnancy test ^b	X		X	X
Adverse events ^c	X	X	X	X
Anti-cancer therapies				X
Olaparib dosing	Continuous twice daily dosing			
Ceralasertib dosing	← Dosing on Days 1-7 only →			
Medication dispensed/returned/medication accountability	X	X		
Survival				X
Optional tumour biopsy at progression ^d		X	(Progression only)	

Visit Name	Subsequent on treatment visits (every 28 days)*	Study treatment discontinued	Follow-up 30 days after last dose of study medication	Survival follow-up
Visit Number	Visit No. 5 onwards			
Day	Cycle X, Day 1			Every 8 weeks
Visit Window	±3d	±7d	+7d	±7d
Blood sample for CCI analysis ^d		X (Progression only)		

^a Safety blood tests must be reviewed prior to dose administration. For a list of all required laboratory tests please refer to Section 5.2.1.
^b Pregnancy tests using blood or urine samples will be performed for women of childbearing potential within 28 days prior to the start of study treatment, on Day 1 of the study prior to commencing treatment, on Day 1 of each subsequent treatment cycle and at the follow-up visit 30 days after last dose of study medication. If results are positive, the patient must be discontinued from the study treatment immediately. Tests will be performed by the hospital's local laboratory.
^c When an AE for nausea and vomiting occurs, an additional eCRF will require completion. All ongoing AEs/SAEs and any new AEs/SAEs identified during the 30 calendar day's follow-up period after last dose of study medication must be followed to resolution.
^d Following the final analysis for PFS for a given stratum the only exploratory samples for that stratum that need to be taken are the required blood sample for CCI analysis at the time of progression and the optional tumour biopsy at the time of progression.

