AZD1775+olaparib treatment arm should be offered the opportunity to escalate the dose of olaparib to 300 mg bd continuing on a 21-day cycle starting at the patient's next treatment cycle. If a patient has had a dose reduction of olaparib due to toxicity on this treatment combination, the investigator may consider a stepwise increment in the olaparib dose at their discretion, e.g. 200 mg, 250 mg then 300 mg. The visit schedule should be followed as per [Table 5](#) at escalation. For patients continuing on olaparib monotherapy at 300 mg bd please follow the toxicity management guidance as per olaparib monotherapy.

For ceralasertib, study treatment can be dose reduced according to the following dose modification table. A maximum of two dose reduction steps are permitted. If after the second dose reduction treatment is not tolerated, no further dose reduction is allowed and study treatment should be discontinued. Once a dose is reduced, re-escalation is not permitted.

Table 11 Ceralasertib+olaparib dose reduction

CCI

Third dose reduction: No further reduction, withdraw patient and treat as clinically indicated.

* Ceralasertib and olaparib may be reduced stepwise within each dose reduction level e.g. dose reduce olaparib first followed by ceralasertib if the adverse event recurs. Dose reductions for anaemia should occur for olaparib first (with consideration to a simultaneous dose reduction in ceralasertib depending on the severity, duration and recurrence of the anaemia). If a dose reduction is required for neutropenia, leukopenia and thrombocytopenia, olaparib and ceralasertib should be dose reduced simultaneously as there is a greater frequency associated with ceralasertib. Once a dose is reduced, re-escalation is not permitted.

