6.8.1 Management of haematological toxicity

6.8.1.1 Olaparib monotherapy and ceralasertib combination (includes patients continuing on olaparib monotherapy randomised to the AZD1775+olaparib arm)

Olaparib monotherapy and ceralasertib+olaparib combination: Complete blood counts will be obtained for all patients at Day 1, 7 and 15 in cycle 1, and then at the beginning of each treatment cycle (Day 1). Complete blood counts must be reviewed prior to dose administration. If hematologic toxicity occurs treatment should be modified as below ([Table 12](#) for Day 1 of each cycle and [Table 14](#) observed at any time during the cycle after Day 1)

and ANC and platelets should be monitored weekly (more often as clinically indicated until recovery). For grade 2 and 4 events please also refer to [Table 14](#). If haematologic parameters do not recover within 28 days, the patient should be removed from the study treatment.

Table 12 Day 1 Haematologic dose modifications and management

Treatment day blood counts and toxicity			
ANC		Platelets	Action
≥1,500/μL	And	≥100,000/μL	No dose modification or interruption
<1,500/μL	Or	<100,000/μL	Delay by 1 week intervals until recovery

Table 13 Management of anaemia

Haemoglobin	Action to be taken
Hb <10 but ≥8 g/dL (CTCAE Grade 2)	
Give appropriate supportive treatment and investigate causality.
 
Investigator judgement to continue study treatment with supportive treatment (eg transfusion) or interrupt dose for a maximum of 4 weeks until recovery to grade 1 or better (≥10g/dL).
 
CCI

Hb <8 g/dL (CTCAE Grade 3)	
Give appropriate supportive treatment (eg, transfusion) and investigate causality.
 
Interrupt study treatment for a maximum of 4 weeks until improved to Hb ≥10 g/dL.
 
CCI

Common treatable causes of anaemia (eg, iron, vitamin B12 or folate deficiencies and hypothyroidism) should be investigated and appropriately managed. In some cases management of anaemia may require blood transfusions. For cases where patients develop prolonged haematological toxicity (≥ 2 week interruption/delay in study treatment due to CTCAE grade 3 or worse anaemia and/or development of blood transfusion dependence), refer to Section 6.8.1.4 for management of this.

6.8.1.2 Olaparib monotherapy and ceralasertib combination: Management of neutropenia, leukopenia and thrombocytopenia (includes patients continuing on olaparib monotherapy randomised to the AZD1775+olaparib arm)

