Table 14 provides guidance for hematologic toxicity (neutropenia, leukopenia and thrombocytopenia) observed any time during the study treatment period. **For Day 1 of each cycle please check the required blood counts to commence treatment in Table 12.**

Table 14 Management of neutropenia, leukopenia and thrombocytopenia

Toxicity	Study treatment dose adjustment
CTCAE Grade 1-2	Investigator judgement whether to continue treatment or dose interrupt. If dose interrupted this should be for a maximum of 4 weeks. All patient should have appropriate supportive treatment and causality investigation.
CTCAE Grade 3-4	Dose interruption until recovered to CTCAE grade 1 or better for a maximum of 4 weeks. If repeat CTCAE grade 3-4 occurrence, CCI [REDACTED] as a second step.

Adverse events of neutropenia and leukopenia should be managed as deemed appropriate by the Investigator with close follow up and interruption of study drug if CTC grade 3 or worse neutropenia occurs.

If a patient has experienced a Grade 3/4 neutropenia, G4 thrombocytopenia, or a dose interruption due to haematological toxicity in a prior cycle, unscheduled Day 8 and Day 15 complete blood counts are required in subsequent treatment cycles. If no further events are experienced in the subsequent 3 consecutive cycles, then the Day 15 CBC visit can be stopped, see Table 4.

Primary prophylaxis with G-CSF is not recommended, however, if a patient develops febrile neutropenia, study treatments should be stopped and appropriate management including G-CSF should be given according to local hospital guidelines. G-CSF should not be used within 24hrs of the last dose prior to dose interruption. Please note that G-CSF should not be used within 24 h of the last dose of study treatment unless absolutely necessary.

Platelet transfusions, if indicated, should be done according to local hospital guidelines.

For cases where patients develop prolonged haematological toxicity (>2 week interruption/delay in study treatment due to CTC grade 3 or worse), refer to Section 6.8.1.4.

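### Table 5 footnote o switches off the Day 8 and Day 15 blood counts that Section 6.8.1.2 requires for the same patients, those moved from AZD1775+olaparib to olaparib alone

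*Protocol*

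**What the plan says.** **Which schedule applies.** Protocol Section 4 says that patients on treatment when the AZD1775+olaparib arm closed may "continue treatment of olaparib monotherapy at their next treatment cycle at the approved dose (300 mg bd) and should follow" Table 5 on a 21-day cycle. The title of Table 5 says that it applies to them. Section 6.8, on raising the olaparib dose, repeats the instruction: "The visit schedule should be followed as per" Table 5 at escalation.

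**What Table 5 says.** Footnote o reads "Unscheduled D8 and D15 visits with complete blood counts should be done from C3 onwards" if a prior cycle brought grade 3/4 neutropenia, grade 4 thrombocytopenia or a dose interruption for haematological toxicity. The Day 15 visit may be dropped after three consecutive event-free cycles. The footnote then ends by retiring itself from version 6.0, with no proviso.

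**What the toxicity sections say.** Section 6.8: "For patients continuing on olaparib monotherapy at 300 mg bd please follow the toxicity management guidance as per olaparib monotherapy". The heading of Section 6.8.1.2 is "Olaparib monotherapy and ceralasertib combination: Management of neutropenia, leukopenia and thrombocytopenia (includes patients continuing on olaparib monotherapy randomised to the AZD1775+olaparib arm)". Its text says that, on the same trigger, "unscheduled Day 8 and Day 15 complete blood counts are required in subsequent treatment cycles". After three event-free cycles, "then the Day 15 CBC visit can be stopped, see Table 4".

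**The concern.** Two live instructions address the same patients and give opposite answers. Footnote o may have been meant to retire only the AZD1775 version of the rule, but it neither says so nor says that the monotherapy rule takes its place. The Section 6.8.1.2 rule does cover these patients, but its cross-reference goes to Table 4, which is the schedule for the other two arms.

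What is at stake is patient safety, not inference. The patients concerned have already had a significant haematological event, in an arm closed partly for increased toxicity, and the protocol lets their olaparib rise from 200 to 300 mg bd, an increase of (300 − 200)/200 = 50%. Table 14 governs toxicity found after Day 1 of a cycle, but it can act only on a count that someone has taken.

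**Working it through.** The plan gives no figure to reproduce. The check sets the provisions side by side and then counts visits.

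**Comparison of the two rules**

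| Feature | Table 5, footnote o | Section 6.8.1.2 |
|---|---|---|
| Patients | Randomised to AZD1775+olaparib, now on olaparib alone (table title, Section 4) | Includes the same patients (section heading, Section 6.8) |
| Trigger | Grade 3/4 neutropenia, grade 4 thrombocytopenia, or haematological dose interruption in a prior cycle | Same |
| Counts | Days 8 and 15 | Days 8 and 15 |
| Easing | Day 15 may stop after 3 event-free cycles | Same |
| Status | Retired from version 6.0 | Required |

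Only the status differs. After Cycle 2 the on-treatment visit in Table 5 is Day 1 of each cycle, so without footnote o the schedule holds no mid-cycle count.

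**Can the conflict be read away?**

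- Section 6.8.1.3 holds the AZD1775 twin of the rule and is retired under a heading that confines it to AZD1775. Footnote o carries no such limit and sits in a table titled for patients already off AZD1775.
- Other Table 5 footnotes say what continues, or on what condition. Footnote f ends triplicate ECGs but keeps single ones. Footnote l lifts the antiemetic restriction only after a 10-day washout. Footnote o does neither.
- Table 4 footnote m keeps the same rule live, but Table 4 covers the olaparib and ceralasertib+olaparib arms.

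**Scheduled counts per affected patient, 21-day cycle, after Cycle 2**

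- Footnote o reading: Day 1 only. 1 count per cycle, 21 days apart. Three cycles: 3 × 1 = 3.
- Section 6.8.1.2 reading: Days 1, 8 and 15. Gaps: 8 − 1 = 7, 15 − 8 = 7, and 22 − 15 = 7 days. Three cycles: 3 × 3 = 9.
- Difference over three cycles: 9 − 3 = 6, or 2 per cycle.
- Once Day 15 is dropped: Days 1 and 8. Gaps of 7 and 22 − 8 = 14 days. Difference: 2 − 1 = 1 per cycle.

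These are nominal days. They leave out the ±3-day visit window and any weekly counts taken until recovery.

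**The case against.** The best reply is that a careful reader can find the operative rule. Section 6.8 separates the visit schedule (Table 5) from toxicity management (the monotherapy guidance). The Day 8 and 15 counts are unscheduled and triggered by toxicity, so they belong to the second. Section 6.8.1.2 names these patients and uses mandatory wording, and retiring footnote o withdraws only that footnote's own rule. This shows what was probably intended. It does not remove the conflict, because Section 4 assigns Table 5 to these patients generally, not only at escalation, and the trail from Section 6.8.1.2 ends at another arm's table.

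The second reply is timing. The arm closed in April 2019 and this version is dated May 2020, so most dose increases will already have happened. If the planning medians of 5 to 6 months for olaparib applied to these patients with exponential PFS, about 2^(−12.5/5) = 18% to 2^(−12.5/6) = 24% of those on treatment at closure would still be progression-free some 12.5 months later, and only those with a qualifying event matter here. The point stands as a limit on numbers. However, the escalation instruction is still in the text, and Tables 5 and 6 still provide for these patients.

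The third reply is that other safeguards remain. AZD1775 is stopped, stepwise escalation is allowed after an olaparib reduction, and counts are reviewed before dosing. Treatment is delayed below the Day 1 thresholds, grade 3–4 events require interruption, and investigators may take extra samples. Section 6.8.1.1 also asks for weekly neutrophils and platelets after toxicity. All of this lowers the risk. The weekly counts, however, run only until the current episode recovers. The routine schedule in Section 6.8.1.1 after Cycle 1 is counts "and then at the beginning of each treatment cycle (Day 1"), so nothing else supplies mid-cycle counts in later cycles.

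**Conclusion.** The concern holds: footnote o is wrong as written. For switched patients with a prior qualifying event, the protocol requires Day 8 and Day 15 counts in one place and withdraws them in another. Following Table 5 as written means 3 scheduled counts over three cycles where Section 6.8.1.2 requires 9, and later 1 per cycle where it requires 2. This is the largest shortfall, since it assumes that the site relies on Table 5 and does not act on Section 6.8.1.2.

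The issue is confined to a closed arm. The documents do not say how many patients are affected, and the number is probably small. The ceralasertib+olaparib versus olaparib comparison of PFS is not affected. It should be corrected because the omitted monitoring is already mandated and the correction is simple.

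**What to change.** 1. In Table 5, replace the last sentence of footnote o with: *The AZD1775-specific rule is retired from CSPv6.0; patients continuing on olaparib monotherapy follow the Day 8/Day 15 count rule in Section 6.8.1.2.*
2. In Section 6.8.1.2, extend the cross-reference to *see Table 4 and Table 5*.

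The cost is two wording edits. Against a site now following Table 5 alone, each affected patient has 2 extra counts per cycle (6 over the first three event-free cycles), then 1 extra per cycle once the Day 15 count is stopped. No new monitoring policy is created, because Section 6.8.1.2 already requires these counts.
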